Appendix B Mayo Score

The Mayo score is a discrete ordinal scale ranging from 0 (normal or inactive disease) to 12 (severe disease) and is a composite of 4 sub-scores: Stool Frequency Sub-score, Rectal Bleeding Sub-score, Endoscopic Finding Sub-score, and Physician's Global Assessment Sub-score, each of which ranges from 0 (normal) to 3 (severe disease).

Mayo Scoring System* for Assessment of Ulcerative Colitis Activity				
Stool Frequency Sub-score				
0	Normal number of stools for study patient			
1	1 to 2 stools per day more than normal			
2	3 to 4 stools more than normal			
3	≥5 stools more than normal			
Rectal Bleeding Sub-score				
0	No blood seen			
1	Streaks of blood with stool less than half the time			
2	Obvious blood with stool most of the time			
3	Blood alone passes			
Endoscopic Finding Sub-score				
0	Normal or inactive disease			
1	Mild Disease (erythema, decreased vascular pattern, mild friability)			
2	Moderate Disease (marked erythema, lack of vascular pattern, friability, erosions)			
3	Severe Disease (spontaneous bleeding, ulceration)			
Physician's Global Assessment Sub-score				
0	Normal			
1	Mild Disease			
2	Moderate Disease			
3	Severe Disease			

Appendix C Ulcerative Colitis Endoscopic Index of Severity

Descriptor (score most severe lesions)	Likert scale anchor points	Definition
Vascular pattern	Normal (0)	Normal vascular pattern with arborization of capillaries clearly defined or with blurring or patchy loss of capillary margins
	Patchy obliteration (1)	Patchy obliteration of vascular pattern
	Obliterated (2)	Complete obliteration of vascular pattern
Bleeding	None (0)	No visible blood
	Mucosal (1)	Some spots or streaks of coagulated blood on the surface of the mucosa ahead of the scope that can be washed away
	Luminal mild (2)	Some free liquid blood in the lumen
	Luminal moderate or severe (3)	Frank blood in the lumen ahead of the endoscope or visible oozing from the mucosa after washing intraluminal blood, or visible oozing from a hemorrhagic mucosa
Erosions and ulcers	None (0)	Normal mucosa, no visible erosions or ulcers
	Erosions (1)	Tiny (≤5 mm) defects in the mucosa of a white or yellow color with a flat edge
	Superficial ulcer (2)	Larger (>5 mm) defects in the mucosa, which are discrete fibrin-covered ulcers when compared with erosions but remain superficial
	Deep ulcer (3)	Deeper excavated defects in the mucosa with a slightly raised edge

NOTE. The worst affected area of the colon visible at sigmoidoscopy was scored. Although the original version of the UCEIS⁶ gave a score of 1 to the normal appearance of a descriptor, a collective decision was made to change the numbering of the levels with normality awarded a score of 0, so that the simple sum of the UCEIS ranges from 0 to 8.

Appendix D Grading of Infusion Reactions

	Grade					
	1	2	3	4		
Signs and	Transient flushing or rash,	Generalized urticaria	Bronchospasm requiring	Anaphylaxis (defined		
symptoms				below); laryngeal/		
	asymptomatic	drug fever >38°C; dyspnea		pharyngeal edema		
	bronchospasm	or reversible	medication; allergy-related	requiring resuscitation;		
		bronchospasm	edema/angioedema;	cardiopulmonary		
				instability requiring		
			symptoms not rapidly	ventilatory support or		
			responsive to interruption	pressors		
			of infusion			
Intervention	None	Infusion held up to 30	Discontinue infusion;	Discontinue infusion;		
		minutes or until symptoms	initiate additional	urgent intervention		
		recede; if symptoms recur	interventions if warranted	indicated		
		upon resuming infusion,	clinically			
		then discontinue infusion				

Anaphylaxis criteria (adopted from the NIAAD/FAAN Clinical Criteria for Anaphylaxis, The Second Symposium on the Definition and Management of Anaphylaxis, Sampson *et al.* 2006): One or both of the following:

- 1. Acute onset of an illness (minutes to several hours) with involvement of the skin, mucosal tissue, or both (e.g., generalized hives, pruritus or flushing, swollen lips-tongue-uvula)

 And at least one of the following:
 - a. Respiratory compromise (e.g., dyspnea, wheeze-bronchospasm, stridor, reduced peak expiratory flow, hypoxemia)
 - b. Reduced blood pressure or associated symptoms of end-organ dysfunction (e.g., hypotonia [collapse], syncope, incontinence)
- 2. Two or more of the following that occur minutes to several hours after exposure to a likely allergen for that patient:
 - a. Involvement of the skin-mucosal tissue (e.g., generalized hives, itch-flush, swollen lipstongue-uvula)
 - b. Respiratory compromise (e.g., dyspnea, wheeze-bronchospasm, stridor, reduced peak expiratory flow, hypoxemia)
 - c. Reduced blood pressure or associated symptoms (e.g., hypotonia [collapse], syncope, incontinence)
 - d. Persistent gastrointestinal symptoms (e.g., crampy abdominal pain, vomiting)

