1.3.2 Allergic and Infusion Reactions

Monoclonal antibodies, including fully human antibodies, can cause allergic or non-allergic infusion reactions when administered intravenously, and three subjects in bertilimumab clinical trials have experienced infusion reactions, one serious. Accordingly, several precautions have been instituted in the protocol to decrease the risk of infusion reactions and possible anaphylaxis, including the administration of study drug^f in a controlled setting with ready availability of antihistamines, fluids, epinephrine, and staff trained in the management of anaphylaxis and a pre-study drug regimen with antihistamines, acetaminophen and corticosteroids.

Grading of infusion reactions will be made according to the criteria set forth in Appendix D, as are criteria for anaphylaxis, by definition, a grade 4 reaction. Management of-study drug infusion in the event of an infusion reaction is set forth in Appendix D as well; if additional interventions beyond interruption of-study drug infusion are indicated, then the investigator should manage the reaction according to his or her clinical judgement and any applicable institutional protocols.

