4.5 REMOVAL, REPLACEMENT, OR EARLY DISCONTINUATION OF SUBJECTS FROM THERAPY OR ASSESSMENT

Subjects are free to discontinue their participation in the study at any time and without prejudice to further treatment. The Investigator must withdraw any subject from the study if that subject requests to be withdrawn, or if it is determined that continuing in the study would result in a significant safety risk to the subject. Withdrawn subjects will not be replaced.

The subject's participation in this study may be discontinued due to the following reasons:

- Subject withdraws consent.
- Intolerable adverse event (any subject experiencing a grade 3 or 4 infusion reaction will be withdrawn from the study).
- Subject's need for medication prohibited by the protocol.

- The Investigator decides that continuing in the study would not be in the subject's best interest.
- The subject is noncompliant with the protocol.
- The subject becomes pregnant.
- Upon the decision of relevant Regulatory Authorities and/or the Institutional Review Board/Independent Ethics Committee (IRB/IEC).

Subjects who progress and/or relapse will be withdrawn from the study at the Investigator's discretion and will be able to receive local standard-of-care.

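### Appendix D: generalized urticaria with dyspnea or reversible bronchospasm fits grade 2 and also the anaphylaxis criteria (grade 4), so two conflicting infusion instructions apply

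*Protocol*

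**What the plan says.** Appendix D has a grade table and, below it, a set of anaphylaxis criteria.

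- **Grade 1** includes "Transient flushing or rash" and "asymptomatic" bronchospasm. No intervention is listed.
- **Grade 2** includes "Generalized urticaria", and "drug fever >38°C; dyspnea" or reversible bronchospasm. The infusion is paused, for at most half an hour or until symptoms settle, and is stopped for good if they return once it is restarted.
- **Grade 4** includes anaphylaxis and refers to the definition under the table. The infusion is stopped and urgent intervention is called for.
- **Anaphylaxis criteria.** Either of two criteria is enough. Criterion 1 is "Acute onset of an illness (minutes to several hours) with involvement of the skin, mucosal tissue, or both", with generalized hives and flushing among the examples, plus at least one further feature. One such feature is "Respiratory compromise (e.g., dyspnea, wheeze-bronchospasm, stridor, reduced peak expiratory flow, hypoxemia".

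Protocol section 1.3.2 refers to Appendix D for grading and for managing the infusion, "as are criteria for anaphylaxis, by definition, a grade 4 reaction". Section 4.5 attaches a study consequence: "any subject experiencing a grade 3 or 4 infusion reaction will be withdrawn from the study".

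**The concern.** A grading scale that drives real-time decisions should give each presentation one grade. Here the signs in the grade 2 cell, taken together, can also satisfy the definition of a grade 4 reaction. Staff who read across the table would pause and possibly restart the infusion. Staff who read the criteria below it would stop the infusion, intervene urgently and withdraw the subject. Someone following the grade 2 cell could thus restart an infusion in a subject who meets the protocol's own definition of anaphylaxis.

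The presentation is foreseeable. Section 5.6.6 names urticaria and bronchospasm among the signs of severe hypersensitivity, and section 1.3.2 reports infusion reactions in three subjects in earlier bertilimumab trials, one of them serious.

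The grade also affects the efficacy data, because it decides who is withdrawn and section 4.5 does not replace withdrawn subjects.

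**Working it through.** No figure in the plan is at stake. The check sets the texts side by side.

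**1. Do the grade 2 signs meet the anaphylaxis criteria?**

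| Presentation | Fits grade 2 cell? | Criterion 1, skin part | Criterion 1, respiratory part |
|---|---|---|---|
| Generalized urticaria + dyspnea | Yes, both signs | Yes (generalized hives is an example) | Yes (dyspnea is an example) |
| Generalized urticaria + reversible bronchospasm | Yes, both signs | Yes | Yes (wheeze-bronchospasm is an example) |

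Both pairs meet criterion 1, assuming acute onset. If study drug is taken as the likely allergen, both also meet criterion 2, which needs two of four features and lists skin and respiratory involvement among them. A skin sign alone or a respiratory sign alone does not meet either criterion, so the overlap arises only when the two occur together.

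**2. What follows from each reading?**

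| | Read as grade 2 | Read as grade 4 |
|---|---|---|
| Infusion | Paused; may restart; stopped if symptoms return | Stopped |
| Urgency | None stated | Urgent intervention |
| Participation (4.5) | No withdrawal required by grade | Withdrawn |

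**3. Does any text settle it?** No visible wording in the grade 2 cell excludes reactions that meet the anaphylaxis criteria, and neither Appendix D nor the protocol body says that the highest matching grade applies. Section 1.3.2 leaves to the investigator's judgement only measures beyond interrupting the infusion, so judgement is not the stated way to choose between pausing and stopping.

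**4. The grade 1 pair.** Flushing is an example under the skin part of criterion 1. Whether bronchospasm without symptoms counts as respiratory compromise is open: the example wheeze-bronchospasm allows it, but the word compromise may imply more. This pair is arguable and is not counted.

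**5. What one withdrawal means for the primary endpoint.** SAP section 6.2.1 carries a full Mayo score to Visit 7 (Day 56) only from within 4 weeks, that is 28 days. Using nominal days, and assuming the early discontinuation visit takes place around the time of the reaction:

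- Reaction at Day 0: 56 − 0 = 56 days, outside the limit.
- Reaction at Day 14: 56 − 14 = 42 days, outside the limit.
- Reaction at Day 28: 56 − 28 = 28 days, exactly at the limit.

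At the planned maximum of 42 subjects randomized 2:1, the arms have 28 and 14 subjects. One subject is 1/28 = 3.6% of the active arm or 1/14 = 7.1% of the placebo arm.

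**The case against.** The strongest reply is that the documents already point one way. The grade 4 cell incorporates the anaphylaxis definition, and section 1.3.2 makes anaphylaxis grade 4 by definition. A site that recognizes the criteria as met and still records grade 2 is arguably not following the protocol. Staff must also be trained in managing anaphylaxis, and section 4.5 requires withdrawal for a significant safety risk whatever the grade. This stands in part: it weakens any claim that two sites could both be right. It does not remove the conflict, because the grade 2 cell still lists both signs and attaches its own infusion instruction to them. The reader has to infer the precedence.

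A second reply concerns the table itself. In the text copy, the grade 1, 2 and 3 cells appear to have lost a line, so a limiting phrase may have stood there. This stands as a caveat; the signs relied on here are visible.

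A reader might also infer more than the documents support:

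- *Every skin and respiratory pairing from grades 1 and 2 is in conflict.* Two skin entries and three respiratory signs give 2 × 3 = 6 pairings. Three of them mix signs from different cells, so no single cell describes them, and the grade 1 pair is arguable. Two are clear.
- *The instructions are opposite.* Both grades interrupt the infusion at first, and grade 2 can also end in discontinuation. They differ on restarting, urgency and withdrawal, so they conflict without being opposites.
- *A safety endpoint is the distribution of grades.* The endpoint in protocol section 2.2.4 and SAP section 7.1 is infusion reactions. The only dedicated output in SAP section 9.3 is a frequency table of skin tolerability.
- *Grade 2 allows a restart at 30 minutes with symptoms persisting.* The cell's reference to recurrence presupposes that symptoms have settled, and grade 3 covers symptoms that respond poorly to interruption. That reading is strained.

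**Conclusion.** The point holds for two presentations: generalized urticaria with dyspnea, and generalized urticaria with reversible bronchospasm. Each fits the grade 2 cell on both signs and also meets anaphylaxis criterion 1, so two grades, two conflicting infusion instructions and two study consequences attach to the same reaction. Section 1.3.2 leans toward grade 4, but no visible text takes these reactions out of grade 2.

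This rests on three assumptions: the onset is acute, the criteria are read as written with no severity threshold, and the source table has no further qualifier. The likely number of affected subjects cannot be estimated, because section 1.3.2 does not say whether any of the three earlier reactions combined skin and respiratory signs. The point merits correction because it bears on patient safety and is cheap to put right. No view is taken here on which clinical instruction is correct.

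**What to change.** 1. Check the original Appendix D table for wording missing from the grade 1 to 3 cells.
2. If no qualifier is there, reconcile the grade cells, the anaphylaxis criteria and sections 1.3.2 and 4.5 so that each presentation has one grade and one infusion instruction.
3. State in Appendix D which part governs when a reaction fits both a lower grade cell and the anaphylaxis criteria, and whether asymptomatic bronchospasm counts as respiratory compromise.

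The sponsor's medical lead decides the clinical content. The cost is a few lines in a short amendment or site memo. The downside is that reactions already recorded may need re-grading, which should be done blind to treatment and documented.

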# **Version History**

Version Number	Date	Revision		
0.1	8 July 2018	Draft		
0.2	6 September 2018	Draft		
0.3	6 January 2019	Draft		
0.4	10 January 2019	Draft		
0.5	13 January 2019	Draft		
1.0	15 January 2019	Final		

# **List of Abbreviations**

	,	
AE	Adverse Event	
CRF	Case Report Form	
CS	Clinically Significant	
FAS	Full Analysis Set	
IV	Intravenous Infusion	
LOCB	Last Observation Carried Backward	
LOCF	Last Observation Carried Forward	
MI	MI Multiple Imputation	
mITT	mITT Modified Intent to Treat	
NCS	CS Non-Clinically Significant	
PD	Pharmacodynamics	
PK	Pharmacokinetics	
PO	Per Os	
PP	Per Protocol	
PPD	Purified Protein Derivative	
SAE	Serious Adverse Event	
SAP	SAP Statistical Analysis Plan	
SOC	OC System Organ Class	
ТВ	Tuberculosis	
TEAE	Treatment-Emergent Adverse Event	
TNF	Tumor Necrosis Factor	
UC	Ulcerative Colitis	
UCEIS	Ulcerative Colitis Endoscopic Index of Severity	

#### 1 Introduction

#### 1.1 General

Ulcerative colitis (UC) is a chronic and relapsing inflammatory disease characterized by diffuse mucosal inflammation limited to the colon and rectum without evidence of any specific causative pathogens.

Bertilimumab is the first monoclonal antibody to specifically neutralize human eotaxin-1 to enter clinical trials. Bertilimumab has been shown to interrupt the eotaxin-stimulated migration of cells and may therefore be useful in the treatment of human diseases such as UC, where eosinophil accumulation is an important feature.

This is the first study investigating clinical outcome of treatment with bertilimumab in UC patients. The purpose of this study is to evaluate the safety and efficacy of bertilimumab compared to placebo in adult patients with active moderate to severe UC. In addition, the pharmacokinetics (PK) and pharmacodynamics (PD) of bertilimumab will be assessed throughout the study.

## 1.2 Study Design Configuration

This is a randomized, double blind, placebo-controlled, parallel group multi-center study in adult patients (18 to 70 years old) with active moderate to severe UC. Eligible subjects will be randomly assigned in a 2:1 ratio to one of two treatment groups, bertilimumab 10 mg/kg or matching placebo, stratified by previous anti-TNF treatment. Approximately the same proportion of subjects who received previous anti-TNF treatment will be included in each arm. Additionally, to reduce bias, the Mayo score and UCEIS will be evaluated by a central reader blind to subject identifier.

The study will consist of three periods:

- A screening period of up to four weeks- Visit 1 (Days -28 to -1)
- A 4-week double-blind treatment period (three IV infusions at two-week intervals) at Visit 2 (Day 0), Visit 3 (Day 14) and Visit 4 (Day 28).

Before each bertilimumab 10 mg/kg or matching placebo treatment, subjects will receive a pretreatment regimen for infusion reaction prophylaxis. The regimen is as follows:

 Dexamethasone 10 mg PO 24-18 hours prior to administration of study drug.

- Acetaminophen 1000 mg PO 1 hour prior to administration of study drug.
- Either loratadine 10 mg PO or cetirizine 10 mg PO one hour prior to the administration of study drug.

If dexamethasone was not administered previously, then 10 mg dexamethasone IV may be administered 1-3 hours prior to study drug administration.

Following completion of pre-dose assessments and administration of pretreatment regimen according to the appropriate timelines above, study drug will be administered by IV infusion over 30 minutes.

• A safety and efficacy follow-up period of approximately 9 weeks- Visit 5 (Day 35), Visit 6 (Day 42), Visit 7 (Day 56) and Visit 8 (Day 90).

#### 2 Centers

This is a multicenter trial. Approximately 10-12 sites in Israel will participate in this study. Additional sites in Europe may be added in the event of slow recruitment.

# 3 Study Objectives

## 3.1 Primary Objective

To evaluate, in patients with active moderate to severe UC, the safety and clinical efficacy of bertilimumab administered as 3 IV infusions over 4 weeks.

## 3.2 Secondary Objectives

To evaluate the pharmacokinetics (PK) and pharmacodynamics (PD) of bertilimumab in patients with active moderate to severe UC.

## 4 Treatment Groups

Bertilimumab (10 mg/kg) or placebo will be administered by intravenous infusion over 30 minutes. A pretreatment prophylactic regimen will be administered prior to dosing on each treatment dosing day (Days 0, 14 and 28) to reduce the likelihood of an infusion reaction.

## 5 Study Schedule

**Table 1 Schedule of Study Events** 

Study Procedures	Screening Period	Treatment Period 			Early Discontinuation	Follow-up Period 				
Visit	1	2	3	4	-	5	6	7	8	
Study Day	-28 to -1	0	14	28	-	35	42	56	90	
Inclusion/exclusion criteria	X	X								
Informed consent	X									
Demographic & medical history	X									
Physical examination	X	$X^*$	$X^*$	$X^*$	X	X	X	X	X	
Vital signs	X	$X^4$	$X^5$	X 	X	X	X	X	X	
ECG	X	$X^5$	$X^6$	$X^6$	X	X	X	X	X	
Screen for active/latent tuberculosis and fecal sample for C. difficile toxin	X									
Randomization	X									
Mayo Score	X				X			X		
Partial Mayo Score	X 	X*	X*	X*	X	X	X	X	X	
Bertilimumab or Placebo infusion- (after administration of pretreatment regimen) 		X	X	X						
Flexible sigmoidoscopy with biopsies 	X				X			X		
Ulcerative Colitis Endoscopic Index of Severity	X				X			X		
Adverse events		X	X	X	X	X	X	X	X	
Concomitant medications	X	X	X	X	X	X	X	X	X	
Infusion reaction assessment 		X	X	X						
Urine β-hCG		$X^*$	$X^*$	X*						
Hematology and biochemistry	$X^9$	$X^*$	$X^*$	X*	X	X	X	X	X	
Serology	X									
PK (bertilimumab) blood sampling		$X^{10}$	$X^{10}$	$X^{10}$	X	X	X	X	X	
Anti-bertilimumab antibodies		X*	$X^*$	X*	X	X	X	X	X	
Eotaxin-1, eosinophil count, eosinophil cationic protein (ECP)-s-CRP		X*	X*	X*	X	X	X	X	X	
Calprotectin in fecal sample	X	X*	X*	X*	X	X	X	X	X	
Eotaxin-1 & eosinophil count in tissue samples	X				X			X		

\* Denotes assessment will be done pre-dose.

<sup>1 Visits during the treatment period have a  $\pm 2$  day window.

<sup>2 At this visit the activities relating to the study period at which time the patient discontinued will be performed.

<sup>3 Visits during the follow-up period have a  $\pm 3$  day window.

<sup>4 Vital signs will be measured pre-dose and 15 min (during), 30 minutes (+15 minutes), 2 hr (± 20 minutes), and 4 hr (± 20 minutes) following initiation of study drug administration.

<sup>5 ECG will be performed pre-dose, and at 30 (+ 15) minutes following initiation of study drug administration.

<sup>6 The pretreatment dosing regimen is as follows: Dexamethasone 10 mg PO 24-18 hours prior to administration of bertilimumab. Acetaminophen 1000 mg PO 1 hour prior to administration of bertilimumab Loratadine 10 mg PO or cetirizine 10 mg PO one hour prior to the administration of bertilimumab. In the event that dexamethasone was not administered previously, then 10 mg dexamethasone IV may be administered one to three hours prior to bertilimumab administration.

At least 3 tissue samples are required from area of active inflammation at Screening. On Day 56 (or early discontinuation visit), at least 3 tissue samples are required from the same region where Screening biopsies were obtained. Additional biopsy samples may be collected at the Investigator's discretion for histological assessment.

<sup>8 Infusion reactions will be monitored for up to 4 hours following study drug administration and graded, as applicable, as appears in Appendix D

<sup>9 Biochemistry will include serum β-hCG at screening.

<sup>10 Blood samples for bertilimumab (PK analysis) will be collected pre-dose, 30 (+15) minutes (immediately post-dose) and 4 hours (± 20 minutes) following initiation of study drug infusion.

<sup>11Partial Mayo Score at Screening will be calculated from the Total Mayo Score.

## 6 Analysis Populations

## **6.1 Safety Analysis Population**

The Safety Analysis Set will include all subjects who were exposed to any of the study treatments (bertilimumab or placebo; i.e. that drug administration data has been collected) and/or prophylactic treatment where applicable (i.e. prophylactic premedication form is completed or prophylactic pre-treatment medication was used, as per the concomitant medication form).

It should be noted that the requirement of prophylactic medications was added as part of the protocol version 8 amendment and, therefore, this information is not available for all subjects in the study.

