2.2 STUDY ENDPOINTS AND OUTCOMES

2.2.1 Efficacy Endpoints

Primary

• Change in Mayo Score from screening to Day 56 (Visit 7). Clinical response at Day 56g will be defined as:

0	A decrease from the pre-treatment screening Mayo score of at least 3 points
	and at least 30%

AND

Protocol: Immune/BRT/UC-01 Page 20 of 58

^f In this protocol, "study drug" refers to either bertilimumab or placebo.

^g This and all other follow-up visits have a window of ± 3 days.

• Either a decrease from the pre-treatment screening sub-score for rectal bleeding of at least 1 point, or Rectal Bleeding Sub-score of 0 or 1.

Secondary

- Change in UCEIS score from screening to Day 56.
- Clinical remission at Day 56, defined as a total Mayo score of 2 points or lower, with no individual sub-score exceeding 1 point.
- Mucosal healing at Day 56, defined as an absolute sub-score for endoscopy of 0 or 1.
- Change in partial Mayo score from Day 0 to all scheduled measurement timepoints (efficacy follow up).

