8.3.1 Analysis Sets

8.3.1.1 Safety Analysis Set

The Safety Analysis Set will include all subjects who were exposed to any of the study treatments.

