8.3.7 Safety Analysis

The evaluation of safety endpoints will be carried out on the Safety set. Safety will be assessed by evaluation of adverse events and changes from baseline in vital signs, physical examination, infusion reactionand clinical laboratory safety test results. Individual subject listing will be provided. The observation period for all the safety endpoints spans from start of study medication up to study day 90.

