8.3.7.1 Adverse Events

Adverse events will be coded to system organ class and preferred term using the latest version of Medical Dictionary for Regulatory Activities (MedDRA) and are graded by the Investigator in terms of severity and relation to study treatment. All data will be listed by subject. Only treatment emergent AEs (TEAEs) will be presented in summary tables.

TEAEs are the adverse events that occur during the observation period, and the pre-treatment adverse events or pre-existing medical conditions that worsen in intensity after start of study medication and within the observation period.

TEAEs will be summarized by treatment arm in terms of crude incidence rates. For each event the crude incidence rate is defined as the number of subjects experiencing the event divided by the number of subjects initially exposed to study drug, regardless of duration of exposure to study drug. In addition, for each event the worst severity grade and the "worst" Investigator's judgment on study drug relationship is considered for each subject and frequency tables by worst severity grade and by worst study drug relation are provided. In this analysis, a subject having experienced more than once events classified under the same preferred term (body system) will be counted only once in the number of subjects with that preferred term (body system).

Summaries of TEAEs will be presented by body system and by preferred term within each body system (MedDRATM Terminology). The percentage of subjects who experienced AEs coded with the same term will be tabulated by treatment group in descending order according to the incidence of AEs in the active treatment groups.

All reported adverse events will be listed independently of their onset date. Serious Adverse Events, causes of death and AEs leading to premature discontinuation of study drug will be summarized similarly and listed. Reasons for premature discontinuation of study drug will be listed and summarized by frequency tables on all analysis sets.

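### SAP 6.1 lets subjects who took only premedication into the safety set; if any exist, they enlarge the TEAE denominator but cannot have a TEAE under the protocol's definition

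*SAP*

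**What the plan says.** **Who is in the safety set.** Protocol 8.3.1.1: "The Safety Analysis Set will include all subjects who were exposed to any of the study treatments". SAP 6.1 starts from the same rule, spells out study treatment as bertilimumab or placebo, and then adds "and/or prophylactic treatment where applicable". The evidence it accepts for that route is that the "prophylactic premedication form is completed or prophylactic pre-treatment medication was used, as per the concomitant medication form". No infusion is required. SAP 6.1 notes that premedication arrived with protocol version 8 and is not recorded for everyone, but gives no reason for widening the set.

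**What counts as study drug.** A footnote to Protocol 1.3.2 says that the term "refers to either bertilimumab or placebo". Premedication is not included.

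**What counts as a TEAE.** Protocol 8.3.7: "The observation period for all the safety endpoints spans from start of study medication up to study day 90". Protocol 8.3.7.1 has two limbs. The first is "TEAEs are the adverse events that occur during the observation period". The second covers earlier events or conditions that "worsen in intensity after start of study medication and within the observation period". The SAP uses the term but does not define it.

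**What the denominator is.** Protocol 8.3.7.1 defines crude incidence as the number of subjects with the event "divided by the number of subjects initially exposed to study drug". SAP 9.3 runs every safety analysis on the SAP 6.1 set and tabulates TEAEs as number and percentage of subjects, with no separate denominator.

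**The concern.** The numerator and denominator of a TEAE rate should describe the same people at risk. Under SAP 6.1 they may not. A subject who took the premedication and was never infused belongs to the safety set but has no observation period, because that period opens with study medication. Such a subject can only lower the rate.

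The sequence is possible under the protocol. Randomization takes place during screening (Protocol 5.1, Appendix A). Oral dexamethasone is scheduled 18 to 24 hours before infusion, and eligibility is reviewed again at Visit 2 on Day 0 (Protocol 5.2). Women of childbearing potential also need a negative urine pregnancy test before each treatment (Protocol 4.1). A subject can therefore be randomized, premedicated and then not dosed.

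Safety is part of the primary objective and the arms are small, so one misplaced subject shows in a percentage. The baseline tables in SAP 9.2 use the same set and would also include the undosed subject, though no bias follows from that alone.

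**Working it through.** The documents state no adverse event rate, expected count or power figure on this point, so there is no planned figure to reproduce.

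**Inputs**

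- Up to 42 subjects, randomized 2:1 (Protocol synopsis, planned sample size): 42 × 2/3 = 28 active and 42 × 1/3 = 14 placebo. This assumes full recruitment and an exact split.
- Withdrawals are not replaced (Protocol 4.5) and randomization precedes premedication, so undosed subjects sit inside the 28 and 14.
- Number premedicated but never infused, *m*, per arm: not in the documents. Assumed range 0 to 2.
- TEAE rate among dosed subjects: not in the documents. 40% is used only as an illustration, because the relative effect does not depend on it.

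**Formula.** With *n* subjects in the arm's safety set and *m* of them never infused:

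reported rate = rate among dosed × (*n* − *m*)/*n*; relative reduction = *m*/*n*.

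| Arm | *m* | Factor | Relative reduction | 40% is reported as |
|---|---|---|---|---|
| Active, n = 28 | 0 | 1 | 0% | 40.0% |
| Active | 1 | 27/28 = 0.964 | 3.6% | 38.6% |
| Active | 2 | 26/28 = 0.929 | 7.1% | 37.1% |
| Placebo, n = 14 | 0 | 1 | 0% | 40.0% |
| Placebo | 1 | 13/14 = 0.929 | 7.1% | 37.1% |
| Placebo | 2 | 12/14 = 0.857 | 14.3% | 34.3% |

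**Effect on the active/placebo ratio of rates** (factor in active ÷ factor in placebo)

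- One such subject, in placebo only: 1 ÷ (13/14) = 14/13 = 1.077.
- Two, in placebo only: 14/12 = 1.167.
- One, in active only: 27/28 = 0.964.

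The ratio can therefore rise or fall.

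**With the protocol's denominator** (*m* removed from *n*), the factor is 1 in both arms and 40% is reported as 40.0%.

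**Which tables are exposed.** The overall TEAE incidence tables in SAP 9.3 are. Summaries by visit and time point are largely not: SAP 9 reports the number of observations, and Protocol 8.3.7.2, 8.3.7.4 and 8.3.7.5 base the numeric laboratory, ECG and vital-sign summaries on subjects with both a baseline and the relevant assessment. An undosed subject contributes little or nothing to them.

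**The case against.** Several points on the other side have force.

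- **Nothing shows that such a subject exists.** A reader might infer that the rates are in fact diluted. The documents support only the conditional statement: with *m* = 0 nothing changes.
- **The argument borrows the protocol's TEAE definition.** If the protocol fills that gap in the SAP, it could equally supply the denominator, and the dilution would disappear. This is a fair reading, since SAP 9.3 states no denominator of its own. But SAP 9.3 directs all safety analyses to the SAP 6.1 set, so a programmer following the SAP would use the wider count. The two documents need to be reconciled whichever reading is preferred.
- **Accounting for everyone given a protocol-mandated regimen is a legitimate aim.** It is, but the wider set does not achieve it in the summaries. Protocol 8.3.7.1 restricts those to TEAEs, and an event in a never-infused subject is not one. Nor would such events be lost under the narrower set, because Protocol 8.3.7.1 lists all reported events whatever their onset and SAP 9.3 plans a by-subject listing with a treatment-emergent flag.
- **The effect is small in a descriptive, exploratory trial.** At an illustrative 40%, one subject moves the rate by 1.4 points (active) or 2.9 points (placebo), less than the weight of a single event (1/28 = 3.6 points; 1/14 = 7.1 points). This stands and sets the grade of the point.

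**Conclusion.** The mismatch between SAP 6.1 and Protocol 8.3.1.1 and 8.3.7.1 is real; its numerical effect is conditional. If at least one subject was premedicated and never infused, the overall TEAE incidence of that arm is understated: by 3.6% (active) or 7.1% (placebo) in relative terms for one subject, and by 7.1% or 14.3% for two. This rests on 28 and 14 randomized, no replacement, the protocol's TEAE definition, and the SAP 6.1 set serving as the denominator.

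Three stronger readings are not supported. Not every safety rate is affected, because by-visit summaries follow observed assessments. The effect is not confined to the rates of version 8 subjects: that version determines who can enter by the premedication route, but rates are tabulated by arm, so any dilution falls on the whole arm. And the mismatch does not systematically favor bertilimumab, since the direction of the contrast depends on which arm the undosed subjects are in. Severity: minor.

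**What to change.** 1. In SAP 6.1, delete the premedication route, so that the safety set is all subjects with a non-missing study-drug administration date. SAP 6.2.1 already uses that rule for the mITT set, and it restores Protocol 8.3.1.1. If the sponsor wants to keep the wider set, then at minimum state in SAP 9.3 that TEAE percentages use only subjects who received study drug, as in Protocol 8.3.7.1.
2. Put the protocol's TEAE definition and observation period in the SAP.
3. Identify premedicated but undosed subjects and their events in the AE listing already planned. The listing of exclusions from each analysis set in SAP 9.1 will show who they are.

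The cost is one clause removed, one definition added and one marker in an existing listing. The downside is that events in premedication-only subjects are listed, not tabulated, but under the protocol's TEAE rule they would not have entered the summary tables anyway.
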